## **8. RESEARCH QUESTION AND OBJECTIVES**

The primary objective of this study is to assess the incidence rate (overall and age stratified) of emergency surgery and major bleeding associated with fracture and trauma among patients to characterize the incidence of relatively homogeneous population who undergo oral anticoagulants (OAC) therapy.

The secondary objective is to estimate the incidence rate (overall and age stratified) of cardiac tamponade or pericardiocentesis occurring during or within one day after conducting a PCI or cardiac ablation procedure.

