#### Definition of terminology

1. Index date: the date of first oral anticoagulant prescription, namely dabigatran, apixaban, rivaroxaban, edoxaban and warfarin
2. Follow-up period: the day after index date to the earliest of treatment discontinuation, , end of continuous enrolment in the database, end of study period, first occurrence of the event of interest, or death.
3. Any OAC treatment discontinuation: treatment gap of any one of OACs for more than 14 days including the time after switch from one OAC to another OAC (primary analysis)

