### **9.3.2      Outcomes**

#### **9.3.2.1     Primary outcomes**

- Outcome name: A combined endpoint of three outcomes; 1) emergency surgery, (2) major bleeding due to fracture (3) major bleeding due to trauma
- Definition: each events will be defined as following:
  - (1) Emergency Surgery defined as any surgical procedure(International Classification of Diseases (ICD) 10 code K000-879) performed on the same day as hospital admission with additional claims associated with urgent fee MDV codes (114701370, 160000210, 180709110)
  - (2) Major bleeding due to fracture  
Any bleeding associated with hospitalization or blood transfusion (ICD10 code E83.111) accompanied by any fracture (M484, M80, S021, S12, S22, S32, S42, S52, S62, S72, S82, S92, T02, T08, T10, T12, T142) listed as the primary diagnosis requiring most medical resource
  - (3). Major Bleeding due to trauma  
Any bleeding associated with hospitalization or blood transfusion (ICD10 code E83.111) accompanied by any trauma (S00-S09, I620, M125, M164, M165, M172, M173, M191, M483, M872, S065, S066, S081, S089, S130, S18, S230, S480, S481, S532, S533, S580, S581, S589, S633, S634, S680, S681, S684, S688, S689, S780, S789, S889, S980, S981, S982, T050, T053, T058, T059, T116, T136, T147, T794, T795, T796, T797, S271, S272, S330, S334, S382, S480, S481, S532, S580, S581, S589, S633, S634, S680, S681) listed as the primary diagnosis requiring most medical resource

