### **9.3.3 Covariates**

These covariates will be used as patient characteristics for the overall population with the primary outcome events.

1. History of stroke or transient ischemic attack yes/no
2. History of myocardial infarction yes/no
3. History of heart failure yes/no
4. History of diabetes mellitus yes/no
5. History of dyslipidemia
6. History of arterial hypertension yes/no
7. History of peripheral artery disease
8. History of kidney impairment
9. History of valvular disease
10. History of liver disease
11. History of dementia
12. History of trauma
13. History of fracture
14. Nursing home resident
15. History of bleeding
16. Charlson co-morbidity index [3]
17. Concomitant medication yes/no for the following:
  - a. aspirin
  - b. clopidogrel
  - c. angiotensin receptor blockers (ARB) or angiotensin converting enzyme inhibitors (ACE)
  - d. beta-blocker
  - e. amiodarone
  - f. calcium-channel blocker (CCB)
  - g. diuretics
  - h. statins
  - i. proton-pump inhibitor
  - j. H2 receptor antagonist

The disease, Charlson co-morbidity index and concomitant medication are defined as [Table 1-Table 4](#). Nursing home resident is defined as MDV codes 113011710, 113016010, 114020910.

Table 1

Definition of clinical history

Disease	Definition	
	ICD10code	prescription
Stroke or transient ischemic attack	I60-I64, G45	-
Myocardial infarction	I21-I23	-
Heart failure	I110, I130, I132, I420, I50	Prescribed furosemide (defined by generic name)
Diabetes mellitus	E100, E101, E109, E110, E111, E119, E14	Prescribed drugs used in diabetes (defined by Anatomical Therapeutic Chemical (ATC) code as A10)
Dyslipidemia	E78	-
Arterial hypertension	I10-I15	Prescribed 2 or more types of anti-hypertensive (defined in Table 2 )
Peripheral artery disease	I702-I709, I71, I739	-
Kidney impairment	N28	-
Valvular disease	I059, I089, I358, I38, I48	-
Liver disease	K70-K77	-
Dementia	F00-F03, G30	-
Trauma	S00-S09, I620, M125, M164, M165, M172, M173, M191, M483, M872, S065, S066, S081, S089, S130, S18, S230, S480, S481, S532, S533, S580, S581, S589, S633, S634, S680, S681, S684, S688, S689, S780, S789, S889, S980, S981, S982, T050, T053, T058, T059, T116, T136, T147, T794, T795, T796, T797, S271, S272, S330, S334, S382, S480, S481, S532, S580, S581, S589, S633, S634, S680, S681	-
Fracture	M484, M80, S02, S12, S22, S32, S42, S52, S62, S72, S82, S92, T02, T08, T10, T12, T142	-

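### Outcomes (2) and (3) do not require the injury or bleed to be new, so an injury already coded before OAC start can be counted as an incident on-treatment event

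*Combined protocol and SAP*

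**What the plan says.** Section 8 sets the target as an incidence rate of "emergency surgery and major bleeding associated with fracture and trauma" in patients on OAC therapy. Section 9.3.2.1 builds outcomes (2) and (3) from three conditions:

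- A bleed: "Any bleeding associated with hospitalization or blood transfusion (ICD10 code E83.111", with the code standing next to the transfusion term.
- An injury code: "accompanied by any fracture" from a list for outcome (2), and for outcome (3) "accompanied by any trauma (S00-S09, I620, M125, M164, M165, M172, M173, M191, M483, M872, S065, S066" and further codes.
- Its position on the claim: "listed as the primary diagnosis requiring most medical resource".

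Section 9.2 (Definition of terminology) defines follow-up as "the day after index date to the earliest of treatment discontinuation" or one of several other end points, among them the first event of interest.

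Section 9.3.3 collects "History of fracture", history of trauma and history of bleeding, with codes in Table 1. Their stated use is descriptive: "These covariates will be used as patient characteristics for the overall population with the primary outcome events".

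**The concern.** An incidence rate should count events that arise during the time at risk. The three conditions say what the admission was for and that there was a bleed. They do not say when the injury happened or whether the bleed is new. A patient with a fracture or head injury coded before the OAC was started, and admitted again after index with a bleed under the same primary diagnosis, meets the definition.

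The study is meant to show how often patients on an OAC face situations in which reversal might be needed. If some counted events continue an injury or bleed that predates the drug, the rates of two of the three primary components, and the combined endpoint through them, overstate that need. Carry-over can add events to the numerator but cannot remove any. The confidence interval does not reflect it, and a larger cohort would not reduce it.

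**Working it through.** **Step 1. The plan's own figures.** There is no sample-size formula to reproduce; section 9.5 states that no formal hypothesis test is planned.

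- Cohort: 7,441 + 23,412 + 16,026 + 12,779 + 3,230 = 62,888, as stated.
- Mean follow-up: 121 / 365.25 = 0.331 year, consistent with the approximately 0.3 year in section 9.5.
- Person-years: 62,888 × 0.3 = 18,866, or 62,888 × 0.331 = 20,834. Section 9.5 expects longer follow-up once time after switching is included, so both are low-end values.

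**Step 2. Does any text require a new injury or bleed?**

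| Place | What it controls | Removes a baseline injury? |
|---|---|---|
| 9.3.2.1, outcomes (2) and (3) | Bleed, injury code, diagnosis position | No |
| 9.2, follow-up | Starts the day after index, stops at the first event in follow-up | No; limits counting to one event per patient |
| 9.2, inclusion and exclusion | Age, NVAF, OAC use, enrolment, index dates | No |
| Abstract, exclusions | Enrolment, dialysis or transplant, valvular disease and related conditions, DVT or PE | No |
| 9.3.3 and Table 1 | History of fracture, trauma and bleeding | No; descriptive only |
| 9.9 and 9.12 | Codes not validated, misclassification | No; carry-over is not mentioned |

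Elsewhere the protocol does control timing. Emergency surgery must fall on the admission day with an urgent-fee code. Tamponade and pericardiocentesis must fall on the same or next day as the procedure. New OAC use needs a clean 6 months. Outcomes (2) and (3) have no comparable condition.

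**Step 3. How far does the bleeding condition protect?** Section 9.3.2.1 gives no list of bleeding codes; its only code there is E83.111, beside transfusion. The one bleeding list in the protocol is the history list in Table 1. It contains S065 and S066, which are also named on the trauma list. (S063 and S064 are on the bleeding list too, and fall within the trauma range S00-S09.) If the history list is used for the outcome, one repeat-coded baseline diagnosis could meet both the bleeding and the trauma condition. For other codes a separate bleed is needed, so the exposure is smaller.

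**Step 4. Size, by assumption only.** The documents give no event rate, no prevalence of baseline injury and no readmission rate for this cohort.

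- If a share *s* of counted events is carry-over, relative inflation = 1/(1 − *s*) − 1. For *s* = 5%, 10%, 20%, 30% this is 5%, 11%, 25%, 43%.
- Example: an assumed true rate of 2.0 per 1,000 patient-years over 18,866 patient-years gives 38 events, or 2.01 per 1,000 (exact Poisson 95% CI 1.43 to 2.76). With *s* = 20% the count is 38/0.8 = 47.5, rounded to 48, or 2.54 per 1,000 (1.88 to 3.37).
- Added events = 62,888 × baseline prevalence × proportion with a qualifying bleeding readmission. With 2% and 0.5%: 62,888 × 0.02 × 0.005 = 6 events, or 0.33 per 1,000 patient-years. With 10% and 3%: 62,888 × 0.10 × 0.03 = 189 events, or 10.0 per 1,000.

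The last range runs from negligible to dominant, and nothing in the documents narrows it.

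**The case against.** The case against has four parts.

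*A bleed is required.* A reader might infer that any readmission for an old fracture or head injury counts as an event. It does not: the text requires a bleed, with the injury as the main resource diagnosis. This stands and narrows the mechanism, most of all for outcome (2). It does not close the gap, because neither condition dates the injury or the bleed, and the bleeding codes are unspecified.

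*The bleed, not the injury, may be the event of interest.* A new major bleed on treatment at a site injured before index is arguably relevant to reversal. This also stands. What must be new is a definitional choice, which is a reason not to replace the main definition. It does not cover a bleed that was itself already coded at baseline.

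*The effect may be lost in sampling error.* In the example above, the inflated 2.54 lies inside the interval around 2.01. That is fair for a single small count, but the direction of the error is fixed, and the pooled cohort may yield more events than assumed.

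*It is partly handled.* The history covariates may show how many patients with events had an earlier injury, and sections 9.9 and 9.12 admit that the codes are not validated. However, a yes/no history does not show whether the event carried the same injury code. Table 1 states no look-back window, and no rate is planned without these patients.

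**Conclusion.** The point holds as a gap in the definition. A bleeding admission after index under a fracture or trauma code already recorded in the 6-month baseline can be counted as incident. Any bias is upward for outcomes (2) and (3) and for the combined endpoint. Emergency surgery has no injury condition and is not affected. The S065/S066 overlap is the sharpest case, on the condition that the bleeding-history list also serves the outcome.

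Two stronger readings are not supported. One is that the primary rates are inflated by a material amount: every percentage above rests on assumed inputs, and the true share could be close to zero. The other is that the main definition must change. Excluding same-category injuries from the main rate would drop genuine second injuries and, unless the denominator were also adjusted, would bias the rate downward. The documents support a check on whether the rates can be read as incident.

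**What to change.** Keep the stated definitions of outcomes (2) and (3) for the main analysis. Add to section 9.7.1 a pre-specified sensitivity analysis of (2), (3) and the combined endpoint:

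- Do not count an event if a code from the same three-character category is recorded in the 6-month baseline.
- Remove patients with such a baseline code from that analysis's person-time for the affected outcome. To keep numerator and denominator on the same patients, leave out all their events for that outcome as well.
- Use the outcome code lists for the look-back, not Table 1, because the fracture history list has S02 where the outcome has S021.
- Say whether the index day belongs to the look-back; it lies between the baseline and the start of follow-up.
- Report the number of events removed beside the main rate, and how many of them matched on category.

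The cost is small. Six months of enrolment before index are already required, and fracture and trauma history is already to be extracted, although the category match needs code-level data and not the yes/no covariate. The restricted rate has limits that should be stated with it. Genuine second injuries in the same category are left out. Injuries coded more than 6 months before index or at hospitals outside the database are still missed.

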## 7. RATIONALE AND BACKGROUND

Until 2002 in Japan, administrative claims data were not standardized or coded electronically. There was limited use for Health Authorities policy decision making or in health research (epidemiological, HTA). Ministry of Health, Labor and Welfare launched the Diagnosis Procedure Combination (DPC) system in 2002 linked with the reimbursement system. DPC is a Japanese version of the Diagnosis Related Groups system; such system is implemented in many countries including UK, US and Germany.

MDV provides commercial claims database consisting of medical records from more than 12.94 million in and out-patients (>80% outpatient claims) from 230 large DPC hospitals as of February 2016.

Dabigatran was the first of the non-warfarin oral anti coagulants (NOACs) to be approved and launched in March 2011 in Japan, then three additional NOACs have been launched for an indication of stroke prevention in patients with non-valvular atrial fibrillation (NVAF). Idarucizumab, a specific reversal agent of dabigatran's coagulation effect, has been launched in November of 2016, and is indicated in dabigatran treated patients who undergo emergency operation or experience life threatening bleeding.

Buchelle et al analysed the German claims database system to calculate the incidence of traumatic brain injury in 65 years or older population, and concluded that 4.8 hospital admissions in 1000 patient year of follow-up, and was found to be higher in nursing home resident with higher morbidity and mortality [1]. Curtis et al reported that fracture annual incidence was 155.3 per 10,000 patient-year in men aged 18-24. For age above 90, the incidence was 224.8 per 10,000 patient-year[2].

There has been no epidemiological assessment to investigate the medical need of reversal in patients undergoing emergency surgery or major bleeding from trauma or fracture receiving NOACs in Japan. The objective of this study is to assess the incidence of emergency surgery and major bleeding associated with fracture and head trauma in Japanese patients prescribed with oral anti-coagulants such as warfarin, dabigatran, apixaban, rivaroxaban and edoxaban.

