Bleeding (gastro-intestinal, etc.)	K25-K29, K922, R04, R31, R58, K250, K260, K270, K280, K290, S063, S064, S065, S066	-

Table 2

Definition of anti-hypertensive

Class/type	ATC code
CCB	C08A0
ARB	C09C0
ACE	C09A0
Diuretics	C03A1, C03A2, C03A3, C03A7, C03A9
Thiazide diuretic	C03A3 (Thiazide, plane), C02D0 (Rauvolfia alkaloids)
Beta blocker	C07A0
Alpha-adrenoreceptor antagonists	C02A2
Potassium-sparing agents	C03A1
Others	C02A1 (Antihypertensives), C02A3 (Antihypertensives for pulmonary arterial hypertension), C09X0 (Other agents acting on the renin-angiotensin system)
Combination agents	C09D1 (ARB and diuretics), C09D3 (ARB and CCB)

Table 3

Definition of disease/conditions and weighted index for Charlson co-morbidity score

Score	Desease/conditions	Definition (ICD-10 code)
1	Myocardial infarct	See Table 1
1	Congestive heart failure	I110, I130, I132, I500
1	Peripheral vascular disease	I70-I74, I77
1	Cerebrovascular disease	I60-69
1	Dementia	See Table 1
1	Chronic pulmonary disease	J40-J47, J60-J67, J684, J701, J703, J841, J920, J961, J982, J983
1	Connective tissue disease	M05, M06, M08, M09, M30-M36, D86
1	Ulcer disease	K221, K25-K28
1	Mild liver disease	B18, K700-K703, K709, K71, K73, K74, K760
1	Diabetes mellitus	See Table 1
2	Hemiplegia	G81, G82
2	Moderate/severe renal disease	I12, I13, N00-N05, N07, N11, N14, N17-N19, Q61
2	Diabetes mellitus with chronic complications	E102-E018, E112-E118
2	Any tumor	C00-C75
2	Leukemia	C90-C96
2	Lymphoma	C81-C85, C88, C90, C96

Table 3 (cont'd)

Score	Desease/conditions	Definition (ICD-10 code)
3	Moderate/severe liver disease	B150, B160, B162, B190, K704, K72, K766, I85
6	Metastatic solid tumor	C76-C80
6	AIDS	B21-B24

Table 4 Definition of concomitant medication

Drug	Definition	
	ATC code	Generic name
Aspirin	-	Aspirin, aspirin dihydroxyaluminum aminoacetate magnesium carbonate
Clopidogrel	-	Clopidogrel sulfate
ARB or ACE	C09A0, C09C0, C09D1	-
Beta blocker	C07A0	-
Amiodarone	-	Amiodarone hydrochloride
CCB	C08A0	-
Diuretics	C03A1, C03A2, C03A3, C03A7, C03A9	-
Statins	C10A1	-
Proton pump inhibitor	A02B2	-
H 2 receptor antagonist	A02B1	-

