## 9.5 STUDY SIZE

This study plans no formal hypothesis testing.

The previous study 1160.279 has identified the patients with confirmed 6 months of baseline period and no OAC treatment (defining “treatment naïve” new starter population). The total of these patients was 62,888. The breakdown by OAC initiated was 7,441 for dabigatran, 23,412 for warfarin, 16,026 for apixaban, 12,779 for rivaroxaban and 3,230 for edoxaban. The average on-treatment follow-up period for pooled OAC in patients with at least one year of baseline period prior to index date excluding the time after switching from one OAC to another was approximately 0.3 year. The average on-treatment follow-up period for pooled

OAC including the time after switching with 6 months of baseline period is unknown, but should be longer than 0.3 year.

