**9.12 BIAS**

- 1. Selection bias: the database is derived from claims arising from DPC hospitals which tend to treat patients with acute and severe disease, and thus may not reflect the general NVAF population of Japan.
- 2. Misclassification bias: outcomes of emergency surgery and bleeding due to fracture/trauma are not validated.

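### I620 sits in both the trauma and the stroke definitions, so a stroke-classed bleed can be counted as major bleeding due to trauma with no S or T injury code

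*Combined protocol and SAP*

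**What the plan says.** Section 9.3.2.1 makes trauma bleeding the third component of a combined primary endpoint. An event is "Any bleeding associated with hospitalization or blood transfusion (ICD10 code E83.111) accompanied by any trauma", and the trauma code must be "listed as the primary diagnosis requiring most medical resource". The code list opens "S00-S09, I620, M125, M164, M165, M172, M173, M191" and goes on with M, S and T codes. No list of bleeding codes is attached to the outcome.

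In Section 9.3.3, the Trauma row of Table 1 repeats the same list, I620 included. The stroke/TIA row of that table is I60-I64 plus G45, and the cerebrovascular item of the Charlson index in Table 3 is I60-69. The history-of-bleeding row of Table 1 reads "K25-K29, K922, R04, R31, R58, K250, K260, K270, K280, K290, S063, S064, S065, S066", which does not contain I620.

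Section 9.9 says that the accuracy of the definitions is unknown, and Section 9.12 adds that "outcomes of emergency surgery and bleeding due to fracture/trauma are not validated". Neither mentions I620. Section 9.2 ends follow-up at the first event of interest.

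**The concern.** The plan gives one code two meanings. As a baseline descriptor I620 marks both stroke and trauma; as an outcome code it marks trauma only. No rule asks for an accompanying injury code, excludes I620, or explains the overlap.

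The cause is what this outcome is meant to isolate. Section 7 states the aim as "major bleeding associated with fracture and head trauma in Japanese patients". Three things are at stake:

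- Stroke-classed bleeds can enter the numerator of the trauma rate and, through it, the combined endpoint.
- An I620 event also ends that patient's follow-up for the outcome, so a later injury-coded bleed would go uncounted.
- A single baseline I620 record scores as history of stroke, history of trauma and a Charlson cerebrovascular point, which blurs the table of patient characteristics.

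**Working it through.** **1. Code overlap.** I expanded each range and compared the lists by code prefix.

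| Trauma list (9.3.2.1) compared with | Codes in common |
|---|---|
| Stroke/TIA, Table 1 (I60-I64, G45) | I620 only |
| Cerebrovascular disease, Table 3 (I60-69) | I620 only |

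I620 is the only code in the trauma list that begins with I. Without it, the trauma list shares nothing with either range.

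**2. Path into the outcome.** The definition needs (a) a bleed with hospitalisation or transfusion and (b) a listed trauma code as primary diagnosis. An admission with I620 in first position meets (b) through that code alone. Whether it meets (a) depends on how a bleed is recognised, which the outcome definition does not say. If the history-of-bleeding row of Table 1 were used, I620 would not satisfy (a) and a further bleeding code would be needed. The text therefore supports saying that such an admission can be counted, not that it always will be.

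**3. Relative size, by assumption.** Let *s* be the share of counted trauma bleeds that are I620-only, and suppose that none of these is traumatic. With person-time held fixed, the overstatement is 1/(1 − *s*) − 1:

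- *s* = 0.10: 1/0.90 − 1 = 0.11, or 11%
- *s* = 0.30: 1/0.70 − 1 = 0.43, or 43%

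These are ceilings for the given *s*, because any I620-only event that really was traumatic reduces them.

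**4. Absolute size, by assumption.** The plan's cohort figure reproduces: 7,441 + 23,412 + 16,026 + 12,779 + 3,230 = 62,888, in line with "The total of these patients was 62,888" in Section 9.5. The only follow-up figure comes from patients with a one-year baseline, "excluding the time after switching from one OAC to another was approximately 0.3 year"; the abstract gives 121 days. Person-time is then 62,888 × 0.3 = 18,866 patient-years, or 62,888 × 121/365.25 = 20,834. Section 9.5 expects longer follow-up in this study, so these figures are low.

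| Assumed I620-only qualifying rate per 1,000 patient-years | Added events at 0.3 year | Added events at 121 days |
|---|---|---|
| 0.5 | 9 | 10 |
| 1 | 19 | 21 |
| 2 | 38 | 42 |
| 5 | 94 | 104 |

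The shares in step 3 and the rates in step 4 are mine, chosen only to show the scale; the documents give neither.

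**The case against.** The strongest reply is that the authors placed I620 under trauma on purpose. It appears by name in both the outcome list and the Trauma row of Table 1, whereas the stroke and cerebrovascular entries catch it only through block ranges. Rows of the history tables are not mutually exclusive either: S065 and S066 are in both the Trauma and Bleeding rows, and S02 in the Fracture row lies inside S00-S09.

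Much of this stands. A reader might infer that I620 is a stroke code and not an injury code. The documents do not support that: they class it as both, and they never describe the code in words. Nor do they show that I620 events are non-traumatic. What remains is that the dual classing is unexplained and that, in the outcome, it works without any injury code. Being both a bleed and a trauma, as with S065, is compatible with a trauma label; being classed as stroke puts the attributed cause in doubt.

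A second reply is that Sections 9.9 and 9.12 already disclose misclassification. They do so in general terms, as unknown code accuracy. They do not tell the reader that a code inside the plan's own stroke range counts as trauma, and this particular overlap can be dealt with before the analysis.

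A third reply is that reversal may be needed whatever the cause. That may be so, but the outcome is reported by cause.

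**Conclusion.** The point holds in a limited form. One code, I620, is classed as trauma and also lies within the plan's stroke and cerebrovascular ranges. An admission with it as primary diagnosis can be counted as trauma bleeding with no S or T injury code. If some of those admissions are not traumatic, the trauma rate and the combined endpoint are overstated. The effect on the combined endpoint is no larger in events, and smaller where the same admission also qualifies as emergency surgery.

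The size is unknown. The 11% and 43% figures are upper limits that assume shares of 10% and 30%, no traumatic event among the I620-only admissions, and fixed person-time. A reader might infer that the trauma rate is inflated by a known amount, or that every I620 admission will be counted. The documents support neither, because they give no I620 frequency and no bleeding code list for the outcome. The overlap is still worth settling before analysis, since it touches a primary outcome and is cheap to resolve.

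**What to change.** In Section 9.3.2.1, count I620 in the main trauma outcome only when an S or T injury code from the trauma list is recorded, in any position, on the same admission. Report I620-only admissions on their own line, and show the trauma rate and the combined endpoint with and without them. In the version without, let follow-up run on past an I620-only admission, so that a later injury-coded bleed can count. Apply the same rule to history of trauma in Table 1, stating what takes the place of the admission for outpatient records.

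The cost is a code-list edit and one or two table rows. The downside is that a traumatic bleed recorded under I620 with no injury code leaves the main count; the separate line shows the most that could be lost in this way. Whether head-trauma codes should have a row of their own is a different question and not part of this change.

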## 4. ABSTRACT

Name of company: Boehringer Ingelheim			
Name of finished medicinal product: Prazaxa			
Name of active ingredient: Dabigatran etexilate			
Protocol date: 18 July 2017	Study number: 1321-0022	Version/Revision: 1.0	Version/Revision date: Not applicable
Title of study:  Medical Need of Non-vitamin K Oral Anti-coagulant Reversal in Japan: Epidemiological Assessment of Emergency Surgery, Major Bleeding due to Trauma and Fracture, using Large Scale Claims Database			
Rationale and background:  There has been no epidemiological assessment to investigate the medical need of reversal in patients undergoing emergency surgery or major bleeding from trauma or fracture receiving oral anticoagulant in Japan. The objective of this study is to assess the incidence of emergency surgery and major bleeding associated with fracture and head trauma in Japanese patients prescribed with oral anti-coagulants such as warfarin, dabigatran, apixaban, rivaroxaban and edoxaban			
Research question and objectives:  The primary objective is to assess, for adult patients initiating an oral anticoagulant for non-valvular atrial fibrillation (NVAF), the incidence rates of emergency surgery, major bleeding due to trauma, and major bleeding due to fracture, overall and stratified by age (<64, 65-74, >75). The secondary objective is to estimate the overall and age stratified incidence of cardiac tamponade and pericardiocentesis.			
Study design:  Non-interventional study based on existing health insurance claims data			

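### The trauma-bleeding outcome accepts eight ICD-10 codes for late effects of earlier injury, with no acute-injury or urgency condition, so non-acute admissions can be counted and can only raise the rate

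*Combined protocol and SAP*

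**What the plan says.** Section 9.3.2.1, outcome (3), is "Any bleeding associated with hospitalization or blood transfusion (ICD10 code E83.111) accompanied by any trauma", where the trauma code must be "listed as the primary diagnosis requiring most medical resource". Most of the list consists of S and T codes, but it also contains "M125, M164, M165, M172, M173, M191, M483, M872". Table 1 in Section 9.3.3 repeats the list to define the baseline covariate for past trauma.

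Two restrictions found elsewhere in the protocol are not applied to outcome (3):

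- **Urgency.** Outcome (1), emergency surgery, needs a procedure "performed on the same day as hospital admission with additional claims associated with urgent fee MDV codes".
- **Bleeding codes.** Table 1 names codes for bleeding history ("K25-K29, K922, R04, R31, R58, K250, K260, K270, K280, K290, S063, S064, S065, S066"), but outcome (3) does not refer to them.

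On scope, Section 7 says the study will "assess the incidence of emergency surgery and major bleeding associated with fracture and head trauma in Japanese patients", and the rationale row of the Abstract also says "major bleeding associated with fracture and head trauma in Japanese patients prescribed with oral anti-coagulants". The title-page objective, the objectives row of the Abstract, Section 8 and Section 9.7.1 all say trauma without restriction. Rates are split by age only.

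**The concern.** Section 7 ties the study to the need for anticoagulant reversal in emergency operations and life-threatening bleeding. An incident trauma bleed should therefore arise from a fresh injury. A list that also defines past trauma at baseline cannot by itself tell a new injury from the late result of an old one. If late-effect codes qualify as the primary diagnosis, a patient admitted for reconstruction of a previously injured joint who bleeds or is transfused may be scored as a trauma bleed. This would put blood loss from non-emergency care into a primary numerator meant to describe unplanned need. The head-trauma wording adds a smaller problem: a reader of the background would expect a rate that the planned tables do not show.

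**Working it through.** **1. The code list.** Outcome (3) has 63 entries, of which 53 are distinct (ten appear twice). The 53 divide as follows:

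| Group | Distinct entries |
|---|---|
| M codes | 8 |
| S00-S09, codes nested in it (S065, S066, S081, S089), and I620 | 6 |
| Other S and T codes | 39 |

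Check: 8 + 6 + 39 = 53.

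**2. Meaning of the eight codes.** The protocol names ICD-10 but prints no labels. In ICD-10, M125 is traumatic arthropathy; M164 and M165 are post-traumatic arthrosis of the hip; M172 and M173 are the same for the knee; M191 is the same for other joints; M483 is traumatic spondylopathy; and M872 is osteonecrosis due to previous trauma. This reading is an assumption to be confirmed in the Japanese code master.

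**3. Does anything else in the rule remove non-acute admissions?**

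- Urgent fee or same-day surgery: required for outcome (1) only.
- Acute-injury condition: none.
- Bleeding code list: none for outcome (3).
- Most-resource diagnosis: an admission for late post-traumatic disease can satisfy it.
- Time at risk: Section 9.2 ends treatment only after a gap of more than 14 days, so an interruption of 14 days or less still counts as on treatment.

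**4. Patient-years.** First, the plan's own cohort size: 7,441 + 23,412 + 16,026 + 12,779 + 3,230 = 62,888, which agrees with Section 9.5. Mean follow-up is about 0.3 year in Section 9.5 and 121 days in the Abstract; 121 / 365.25 = 0.331 year.

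- 62,888 × 0.3 = 18,866 patient-years
- 62,888 × 121 / 365.25 = 20,834 patient-years

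Both are lower guides at this cohort size. The 0.3-year figure excludes time after switching, and Section 9.5 expects follow-up in this study to be longer.

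**5. Effect of one miscounted event.** Added rate = 1,000 / patient-years.

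- 1,000 / 18,866 = 0.053 per 1,000 patient-years
- 1,000 / 20,834 = 0.048 per 1,000 patient-years

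Ten such events would add 0.48 to 0.53. Follow-up stops at the first event, so a miscounted event either adds to the numerator or, if a true event would have come later, shortens the patient's time at risk. Either way the rate rises.

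**6. Illustration.** The documents give neither a trauma-bleeding rate nor the share of events under M codes, so both are assumed here. Intervals are exact Poisson, with lower limit χ²(0.025; 2e)/2 and upper limit χ²(0.975; 2e+2)/2, each divided by 18,866 patient-years.

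| Assumed rate per 1,000 | Events, full list | 95% CI | Assumed M share | Events left | Rate (95% CI) |
|---|---|---|---|---|---|
| 2 | 38 | 1.43–2.76 | 5% | 36 | 1.91 (1.34–2.64) |
| 2 | 38 | 1.43–2.76 | 20% | 30 | 1.59 (1.07–2.27) |
| 5 | 94 | 4.03–6.10 | 20% | 75 | 3.98 (3.13–4.98) |

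A small share would hardly matter. A 20% share would lower the reported rate by about a fifth.

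**The case against.** The strongest reply is that the rule still requires a bleed. On its natural reading, hospitalization or transfusion qualifies a bleed and is not an event by itself, and the listed code must also be the primary diagnosis. A reader might infer that every planned operation with a transfusion is scored as a trauma bleed. The text does not support that. Because bleeding is not defined by code, it leaves open whether operative blood loss qualifies, so such cases can be counted but need not be. Deleting eight codes does not close that gap.

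A reader might also argue from the chapter letter, since Table 3 uses M codes for connective tissue disease ("M05, M06, M08, M09, M30-M36, D86"). That argument fails because the fracture outcome in the same section accepts M484 and M80. The point rests on what the eight codes mean in ICD-10, not on their chapter.

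Three further inferences go too far:

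- That the bias is largest in older patients: nothing in the documents shows this.
- That the cited 4.8 per 1,000 is a yardstick for its size: that figure is brain-injury admissions at age 65 or older in Germany, not major bleeds in anticoagulated patients.
- That the study fails its stated aim on head trauma: the term appears only in rationale text, and every formal objective says trauma.

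Sections 9.9 and 9.12 do concede that the codes are unvalidated. That general caveat covers unknown coding accuracy. It does not cover codes that, even when correctly recorded, do not denote a new injury.

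**Conclusion.** The concern holds in conditional form. As written, outcome (3) can admit bleeding in admissions for late post-traumatic disease, and the error can run only upward. The conclusion rests on the standard ICD-10 meaning of the eight codes. Its size is about 0.05 per 1,000 patient-years per event on the planning figures, and somewhat less if follow-up is longer, as Section 9.5 expects. The number of such events is unknown and may be small. The change is worth making because it affects a primary rate and can be made before the analysis. The head-trauma wording is a lesser inconsistency to reconcile.

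**What to change.** 1. Confirm the labels of the eight codes in the Japanese code master.
2. Remove M125, M164, M165, M172, M173, M191, M483 and M872 from outcome (3) for the main analysis. Keep them in the Table 1 history covariate, where a past injury is what is meant.
3. Report the outcome (3) rate with the full list, as it now stands in Section 9.3.2.1, as a sensitivity analysis, so that the contribution of the eight codes is visible.
4. Align the Abstract rationale and Section 7 with the formal objectives. Alternatively, report head trauma (S00-S09) and other trauma as two rows beside the total, stating which row takes I620.

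The cost is one code-list edit, one sensitivity result and at most two table rows, with no new data. The downside is the possible loss of a few acute injuries coded this way, which the sensitivity analysis would show.
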